## 5.5 Demographic and Other Baseline Characteristics

### 5.5.1 Demographic and Baseline Characteristics

The following demographic and baseline characteristics will be summarized by descriptive statistics (Analysis population: ITT):

- Age at time of informed consent (in years, as a continuous variable)
- Age category ( $\leq 65$ ,  $> 65$  years)
- Gender (Male, Female)
- Race (White, Black or African American, Asian, American Indian or Alaska Native, Hawaiian Native or Other Pacific Islander, Other)
- Country
- Weight at baseline (in kilograms)
- Height at screening (in centimeters)
- BMI ( $\text{kg}/\text{m}^2$ ) calculated using weight and height at screening  
 $\text{BMI } (\text{kg}/\text{m}^2) = \text{weight } (\text{kg}) / \text{height } (\text{m})^2$
- Presence or absence of background of atopy
- Baseline average and peak pruritus NRS (weekly average during the 7 days prior to day 1, as a continuous variable)
- Purigo baseline Assessment (PAS)
- IGA
- Number of nodules on the entire body

Stratification factors include country and presence or absence of background of atopy. A summary table for presence or absence of background of atopy will be provided to show any discrepancies between what was reported through Interactive Voice Response System (IVRS)/Interactive Web Response System (IWRS) versus eCRF data (at baseline visit). Country and background of atopy will be used as a cofactor in the primary and secondary efficacy endpoint analyses.

By-subject listings of demographic data and other baseline characteristics (as summarized above) will be provided.

### 5.5.2 Medical History

Medical history from the screening visit will be summarized by treatment group and overall. Medical history will be coded using the MedDRA version 19.0. The number and percentage of subjects experiencing at least one such diagnosis will be summarized by the MedDRA system organ class (SOC) and preferred term (PT) (Analysis population: ITT).

Summary (n, %) may be presented according to MedDRA groups for specific MH analyses (such as asthma, food allergy, allergic conjunctivitis, etc.).

By-subject listings of medical history will be provided.

### 5.5.3 Prior and Concomitant Therapies

Start and stop dates of medications or medical and surgical procedures will be compared to the date of first dose of study drug to allow them to be classified as either Prior or Concomitant. Medications or medical and surgical procedures that start and stop prior to the date of first dose of study drug will be classified as Prior.

If start and/or stop dates of medications or medical and surgical procedures are missing or partial, the dates will be compared as far as possible with the date of first dose of study drug. Medications or medical and surgical procedures will be assumed to be Concomitant, unless there is clear evidence (through comparison of partial dates) to suggest that they started and stopped prior to the first dose of study treatment. If there is clear evidence to suggest that the medication or medical and surgical procedure started and stopped prior to the first dose of study drug, they will be assumed to be Prior.

#### **Missing date information for prior and concomitant medications**

For prior and concomitant medications, incomplete (i.e., partial missing) start dates and/or stop dates will be imputed. When the start date and the stop date are both incomplete for a subject, the start date will be imputed first.

#### ***Incomplete start date***

The following rules will be applied to impute the missing numeric fields for an incomplete prior or concomitant medication start date. If the stop date is complete (or imputed) and the imputed start date is after the stop date, then the start date will be imputed using the stop date.

#### **Missing Month and Day**

- If the year of the incomplete start date is the same as the year of the first administration of the study drug, then the month and day of the first administration of the study drug will be assigned to the missing fields.
- If the year of the incomplete start date is before the year of the first administration of the study drug, *December 31* will be assigned to the missing fields.
- If the year of the incomplete start date is after the year of the first administration of the study drug, *January 1* will be assigned to the missing fields.

#### **Missing Month Only**

- If only the month is missing, then the day will be treated as missing and both the month and the day will be replaced according to the procedure above.

### Missing Day Only

- If the month and year of the incomplete start date are the same as the month and year of the first administration of the study drug, then the day of the first administration of the study drug will be assigned to the missing day.
- If either the year of the incomplete start date is before the year of the date of the first administration of the study drug or if both years are the same but the month of the incomplete start date is before the month of the date of the first administration of the study drug, then the last day of the month will be assigned to the missing day.
- If either the year of the incomplete start date is after the year of the date of the first administration of the study drug or if both years are the same but the month of the incomplete start date is after the month of the date of the first administration of the study drug, then the first day of the month will be assigned to the missing day.

If the stop date is complete and the imputed start date as above is after the stop date, then the start date will be imputed by the stop date.

### Incomplete stop date

The following rules will be applied to impute the missing numeric fields for an incomplete prior or concomitant medication stop date. If the date of the last administration of the study drug is missing, then replace it with the last visit date in the imputations described below. If the imputed stop date is before the start date (imputed or non-imputed start date), then the imputed stop date will be equal to the start date.

### Missing Month and Day

- If the year of the incomplete stop date is the same as the year of the last administration of the study drug, then the month and day of the last administration of the study drug will be assigned to the missing fields.
- If the year of the incomplete stop date is before the year of the last administration of the study drug, *December 31* will be assigned to the missing fields.
- If the year of the incomplete stop date is after the year of the last administration of the study drug, *January 1* will be assigned to the missing fields.

### Missing Month Only

- If only the month is missing, then the day will be treated as missing and both the month and the day will be replaced according to the above procedure.

### Missing Day Only

- If the month and year of the incomplete stop date are the same as the month and year of the last administration of the study drug, then the day of the last administration of the study drug will be assigned to the missing day.
- If either the year of the incomplete stop date is before the year of the date of the last administration of the study drug or if both years are the same but the month of the incomplete stop date is before the month of the date of the last administration of the study drug, then the last day of the month will be assigned to the missing day.
- If either the year of the incomplete stop date is after the year of the date of the last administration of the study drug or if both years are the same but the month of the incomplete stop date is after the month of the date of the last administration of the study drug, then the first day of the month will be assigned to the missing day.

#### 5.5.3.1 Prior and concomitant medications

Prior and concomitant medications will be coded using the World Health Organization Drug Dictionary (WHODD), version March 2016 E B2.

Prior and Concomitant medications will be summarized separately by Anatomical Therapeutic Chemical (ATC) level 2, level 3, and preferred name in frequency tables (Analysis population: ITT). Subjects with more than one medication in a given ATC level and preferred name will be counted only once in that category. The following summaries will be produced:

- Number and percentage of subjects who had Prior medications by ATC level 2, level 3, and preferred name
- Number and percentage of subjects who had Concomitant medications by ATC level 2, level 3, and preferred name

A by-subject listing of all prior and concomitant medications will be provided.

#### 5.5.3.2 Prior and concomitant medical and surgical procedures

Medical and surgical procedures will be coded using the MedDRA version 19.0.

Prior and Concomitant medical and surgical procedures will be summarized separately by SOC and PT in frequency tables (Analysis population: ITT). Subjects with more than one procedure in a given SOC and PT will be counted only once in that category. The following summaries will be produced:

- Number and percentage of subjects who had Prior medical/surgical procedures by SOC and PT
- Number and percentage of subjects who had Concomitant medical/surgical procedures by SOC and PT

A by-subject listing of all prior and concomitant medical and surgical procedures will be provided.

#### 5.5.3.3 Rescue therapies

Rescue treatments for pruritus could be added to the study drug from Day 29. In that case, all efficacy and safety assessments should be completed before starting the rescue treatments. The number and percentage of subjects initiating use of rescue therapies will be summarized overall and by preferred name (for rescue medications) or preferred term (for rescue procedures) for all subjects in the ITT population. Rescue medication will be summarized by topical and systemic groups. Subjects with more than one rescue therapy in a given preferred name or preferred term will be counted only once in that category.

By-subject listings of all rescue therapies will be provided.

### 5.6 Treatment Compliance

Subject compliance with study treatment will be assessed via relative injections volume (%) of study drug. Refer to Section 5.8.1 for more analyses.

Actual Total Volume (mL) is defined as the sum of the real volume injected according to the case report form records.

Prescribed Total Volume (mL) is defined as number of total injections *Type equation here.* (Weight of the subject in kg x 0.02 ml/Kg)).

Compliance Rate (%) is defined as

$$(\text{Volume}(mL) \text{ of actual injections} / \text{Volume of planned injections}) \times 100$$

A Subject is study medication compliant if the compliance rate is between 80% and 120%..

### 5.7 Efficacy Evaluation

Primary inference for efficacy analysis will be the percent change from baseline in NRS to week 4 (weekly average of the peak). This analysis will be based on the ITT population, and repeated using the PP population. Primary imputation method for any missing data including those who took rescue medication as failure will be the LOCF (last observation carried forward) approach. In addition, Multiple Imputation (MI) using the missing at random assumption will be conducted on ITT population:

### 5.7.1 Analysis and Data Conventions

This study is designed to test for superiority. Appropriate statistical tests to assess the superiority of nemolizumab should be performed, with the null hypothesis being: there is no difference between nemolizumab and placebo treatments and the alternative hypothesis: there is a difference between treatments in reducing the pruritus as major symptom of PN at week 4.

#### 5.7.1.1 Multi-center Studies

For the purpose of the summaries and analyses, the term 'Center' will be used to define each investigator site. All sites within the country (France, Germany, Poland and Austria) will be pooled together in the efficacy analyses. If the country is found to be a significant factor in ANOVA or ANCOVA models the evaluation of the consistency of treatment effects across countries will be performed via subgroup analysis (see Section 5.7.1.6).

#### 5.7.1.2 Adjustments for Covariates

The primary and secondary efficacy analyses will be adjusted for the following baseline covariates:

- Presence or absence of background of atopy (the stratification factor for randomization to the treatments),
- Country

Additional covariates will be used as follows:

- Absolute change from baseline to any visits of the weekly average of the peak and of the average pruritus NRS will use the same factors as the percent change but will also include baseline NRS as a covariate.
- Absolute change and shift from baseline to each visit in Dermatology Life Quality Index (DLQI) will include baseline DLQI, background of atopy, and country as covariates.

#### 5.7.1.3 Handling of Missing Data

**Use of rescue therapy:** For the purpose of efficacy analysis, subjects receiving any rescue therapies will be considered as treatment failures. All efficacy data, except Observed Case (OC), will be set to missing after rescue medication is used. In OC analysis, observed data after subject has received rescue treatment will be included.

**Diary data:** If a subject has less than 5 diary entries in a week, the weekly prorated average scores will be set to missing. Otherwise the method of computing weekly score when data are missing will be mean replacement approach. i.e. calculation of the overall weekly score a given week as 7 times average of non-missing average of that week.

The following methods will be used to impute the missing values:

**Continuous endpoints:** To impute the missing values for the primary and secondary endpoints, the following imputation approaches will be carried out to assess the robustness of study conclusions with choice of imputation method.

For sensitivity analyses, continuous endpoints will be analysed using analysis of covariance (ANCOVA) including terms of treatment group, country, presence or absence of background of atopy (the stratification factor for randomization to the treatments) and the corresponding baseline value.

1. **Last Observation Carried Forward (LOCF):** The primary imputation method for any missing data will be the LOCF approach. The last observed post-baseline value will be used to replace missing values for continuous variables. For questionnaire-based variables, LOCF will be applied to missing individual questions first, and the value of the total (or sub-scale) score will be derived based on the imputed individual questions.
2. **Observed Case (OC):** No data will be imputed. The observed values are used in analysis, including assessments post rescue medication.
3. **Multiple imputation (MI) method under assumption missing at random (MAR):**

Multiple Imputation (MI) using the Missing At Random (MAR) assumption will also be used. The MI procedure of the SAS system will be used to generate five sets of data with missing values imputed from observed data. It is expected that the pattern of missing data will be monotonic, with slight deviations being corrected by the Markov Chain Monte Carlo (MCMC) method of the MI procedure. Linear regression will be employed to model the missing NRS score, with the following covariates included in the imputation model: treatment and non-missing data from earlier timepoints.

- **Analysis phase:** The imputed datasets will be analyzed using the methodology described for percent change from baseline in NRS score.
- **Pooling phase:** The results from the analysis of the multiple imputed datasets will be combined by the MIANALYZE procedure of the SAS system.

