## 4.2 Efficacy and Safety Variables

### 4.2.1 Efficacy Variables

#### 4.2.1.1 Pruritus Numeric Rating Scale (NRS)

Pruritus NRS is a scale to be used by the subjects to report the intensity of their pruritus (itch) during the last 24 hours all along the study from first screening visit to the follow-up visit. Subjects will receive instructions on how to record their pruritus NRS scores on an electronic device and will complete the assessment once daily at home in the evening throughout the clinical trial (including the follow-up period).

Subjects will be asked the following questions in their local language:

- For average itch intensity: “On a scale of 0 to 10, with 0 being ‘no itch’ and 10 being ‘worst itch imaginable’, how would you rate your itch overall during the previous 24 hours?”
- For maximum (Peak) itch intensity: “On a scale of 0 to 10, with 0 being ‘no itch’ and 10 being ‘worst itch imaginable’, how would you rate your itch at the worst moment during the previous 24 hours?”

Weekly prorated average score will be calculated and used in the analysis. If a subject has less than 5 diary entries in a week, the weekly average scores will be set to missing. Refer to Section 5.2 for classification of diary data into analysis week/visit.

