### 4.2.2 Efficacy endpoints

#### 4.2.2.1 Primary endpoint

Percent change from baseline in NRS to week 4 (weekly average of the peak).

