#### 4.2.2.2 Secondary efficacy endpoints

- Absolute and percent change from baseline in weekly average of the peak and average pruritus NRS to each visit
- Absolute and percent change from baseline in weekly average of the peak and average VRS to each visit
- DPS at hours 24, 48, and 72 for baseline and Week 4 visits
- Absolute change from baseline in PAS Item 5 (number of lesions) to each visit

- PAS Item 6 (excoriation/crusts and healed lesions stages) at each visit
- IGA at each visit
- Proportion of subjects achieving IGA success (defined as IGA=0[clear] or IGA=1[Almost clear] with two-point improvement from baseline) at Week 12

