### **Baseline**

‘Baseline’ is defined as the last available assessment prior to the first planned study drug. The date of the first planned study drug refers to date of the first actual administration of study drug at visit V3/Baseline/Day 1 if exists; otherwise, date of randomization.

For diary data (pruritus NRS, VRS, Sleep disturbance NRS), the baseline values will be derived from data collected during the 7 days prior to the first planned study drug. Baseline score will be the weekly prorated average of non-missing subject diary scores reported during the 7 days. A minimum of 5 daily scores out of the 7 days is required to calculate the weekly prorated average score.

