**Analysis Visit**

Study day is relative to date of randomization. Day -1 is the day before randomization, and day 1 is date of randomization.

Assessments at early termination and unscheduled visits will be slotted based on the following visit window.

Period	Analysis Visit	Target day (relative to randomization)	Day ranges
Screening Period	Screening 1	-28	-28 to -8
	Screening 2	-7	-7 to -1
Treatment	Baseline	1	≤1
	Week 1	8	2-11
	Week 2	15	12-22
	Week 4	29	23-43
	Week 8	57	44-71
	Week 12	85	72-99
Follow-up	Week 16	113	100-119
	Week 18	126	>119

The diary reported during study will be classified into analysis visits as follows (i.e., during the 7 days prior to the target day of analysis visit. In this case, the target day of analysis visit is relative to date of the first planned study drug.):

- Day -7 to -1 = Baseline
- Day 1 to 7 = Week 1
- Day 8 to 14 = Week 2
- Day 22 to 28 = Week 4
- Day 50 to 56 = Week 8
- Day 78 to 84 = Week 12
- Day 106 to 112 = Week 16
- Day 120 to 126 = Week 18

These analysis visits will be used in the calculations for all week-based parameters collected on subject's diary (e.g., pruritus NRS, VRS, Sleep disturbance NRS, PAS, DPS, DLQI) Other non-diary data, such as , IGA, vital signs, body weight, clinical laboratory assessments, respiratory assessment/PEF, will be analyzed according to actual scheduled visits.

For efficacy and safety data (except clinical laboratory assessments), where two or more assessments (include both scheduled and unscheduled assessments) are available for the same visit interval, the one closest to the target visit date will be used for the summary and analyses. For clinical laboratory assessments, if repeated measurements are taken for either time point (scheduled visit), then the last measurement will be used for the value for that time point. Unscheduled labs will be included in listings, but not summaries of the data. All post baseline assessments, including repeated or unscheduled visits, will be used for potentially clinically significant value (PCSV) determinations.

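### SAP 5.7.1.3 scores a diary week with 5 or 6 entries as a weekly total (seven times the daily mean), although the endpoints are defined on a weekly average

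*SAP*

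**What the plan says.** SAP 5.7.1.3 (Diary data) deals with incomplete weeks in two steps. With fewer than five entries, "the weekly prorated average scores will be set to missing". For the remaining incomplete weeks, the SAP states that "the method of computing weekly score when data are missing will be mean replacement approach", which it then spells out as "calculation of the overall weekly score a given week as 7 times average of non-missing average of that week". The second step therefore governs weeks with 5 or 6 of 7 entries.

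Elsewhere the SAP works with an average:

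- SAP 4.2.1.1 (pruritus NRS): "Weekly prorated average score will be calculated and used in the analysis". The same statement appears for the VRS (4.2.1.2) and the sleep disturbance NRS (4.2.1.6).
- SAP 5.2, Baseline: "Baseline score will be the weekly prorated average of non-missing subject diary scores reported during the 7 days". There is no factor of 7, and the same minimum of five days applies.
- SAP 4.2.2.1 and 5.7.2: the primary variable is the percent change to Week 4 in the weekly average of peak pruritus.
- SAP 4.2.2.2: "Absolute and percent change from baseline in weekly average of the peak and average pruritus NRS to each visit".

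The diary window for the primary time point is "Day 22 to 28 = Week 4" (SAP 5.2, Analysis Visit).

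**The concern.** The formula for an incomplete week and the quantity to be analysed are on different scales. A programmer looking up what to do with one or two missing diary days will go to 5.7.1.3, and the formula there returns a total.

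The sentence fixes the primary Week 4 value for any subject missing one or two of Days 22 to 28. An incomplete Week 1 or Week 2 reaches the primary endpoint only if that week is carried forward (LOCF, the primary imputation method) or enters the multiple imputation. Followed literally, a Week 4 total would be set against a baseline average, and subjects with complete and incomplete weeks would be on different scales within the same analysis.

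**Working it through.** The plan prints no worked weekly score, so there is no figure of its own to reproduce. The sample size is not touched by this point.

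**Inputs**

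- Daily peak NRS from 0 to 10 (SAP 4.2.1.1); daily VRS from 0 to 4 (SAP 4.2.1.2).
- At least 5 of 7 entries needed (SAP 5.7.1.3).
- Baseline is the average of the non-missing days (SAP 5.2).
- Mean baseline peak NRS at least 7 (Protocol 5.3).
- 35 subjects per group and an assumed treatment difference of 30 percentage points (SAP 5.10).
- The individual scores below are illustrations, not trial data.

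**1. What the formula returns.** Take five entries 6, 5, 4, 7, 5. Their mean is 27/5 = 5.4. Filling the two empty days with 5.4 gives a seven-day sum of 27 + 10.8 = 37.8, which equals 7 × 5.4. Dividing by 7 returns 5.4. The rule as written stops at 37.8. Its maximum is 7 × 10 = 70 for the NRS and 7 × 4 = 28 for the VRS.

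**2. Percent change, incomplete Week 4 as a total against a baseline average.** If the true percent change is p, the computed one is 7 × (100 + p) − 100 = 600 + 7p.

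| True change | Computed as written |
|---|---|
| 0% | +600% |
| −37.5% (8 to 5) | +337.5% |
| −50% (8 to 4) | +250% |
| −87.5% (8 to 1) | −12.5% |

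For comparison, the largest increase that the scale allows from a baseline of at least 7 is (10 − 7)/7 = +42.9%.

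**3. Absolute change, same mixture.** With baseline b and true change a, the computed change is 7(b + a) − b = 6b + 7a. For 8.0 to 4.0 this is 48 − 28 = +20.0 instead of −4.0. The largest real increase is 10 − 7 = +3.0.

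**4. When a range check would miss it.** The total stays within 0 to 10 when 7m ≤ 10, so when the recorded-day mean m is at most 1.43. That is an improvement of at least 1 − 1.4286/7 = 79.6% from a baseline of 7, or 1 − 1.4286/10 = 85.7% from a baseline of 10. In the 8.0 to 1.0 example the Week 4 value would read 7.0, which looks plausible.

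**5. Weight of one subject.** The 8-to-5 subject moves by 337.5 + 37.5 = 375 percentage points. In an arm of 35 that shifts the mean by 375/35 = 10.7 points, against the assumed effect of 30.

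**6. If totals were used consistently in every week.** For 8.0 to 4.0 the percent change is (28 − 56)/56 = −50%, as it should be. The absolute change is 28 − 56 = −28.0 instead of −4.0, seven times too large.

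**The case against.** The strongest reply is that the analysed quantity is settled elsewhere. SAP 4.2.1.1, 4.2.1.2 and 4.2.1.6 say that the prorated average is what enters the analysis. The baseline definition shows what that term means, with the same five-day minimum and no factor of 7. The sentence immediately before the formula also speaks of averages. On this reading, seven times the observed mean is a correct intermediate total under mean replacement, the final division was simply left unwritten, and no one would put a value of 28 into an analysis of a 0-to-10 score. The independent output checks in SAP 5.1 add a safeguard.

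Much of this stands. An average is the likely intent, baseline is not in doubt, and a team that follows 4.2.1.1 and 5.2 will get the right values. The consistent-totals case in step 6 also conflicts with the baseline definition and with the formula's restriction to incomplete weeks, so it serves only to show that the primary percent change would survive it.

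What the reply does not supply is the missing step. Section 5.7.1.3 holds the only explicit post-baseline formula for a week with 5 or 6 entries. The variable definitions use the term prorated average without giving a calculation, and SAP 5.2 gives one for baseline only. The protocol has no rule for partly missing post-baseline weeks, and its section 9.2 leaves such conventions to the SAP. The formula is presented as the weekly score itself, not as an intermediate quantity.

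**Conclusion.** The concern holds. The sentence in SAP 5.7.1.3 gives a weekly total where the SAP analyses a weekly average, and it should be corrected because it belongs to the derivation of the primary endpoint. It is a wrong sentence, not evidence that an analysis on a 0-to-70 scale is planned.

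The per-subject error under literal coding is exact: 600 + 7p for percent change and 6b + 7a for absolute change, given an incomplete Week 4 and a baseline average. How many subjects would be affected, and in which direction the treatment comparison would move, cannot be derived, because the documents do not say how often a week has 5 or 6 entries. If the code follows the other sections, the results are unaffected. If it follows this sentence, most errors would be conspicuous, but those from recorded-day means of 1.43 or less could pass a range check.

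**What to change.** In SAP 5.7.1.3, remove the factor of 7 and replace the explanatory clause with:

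> Weekly score = arithmetic mean of the non-missing daily scores when at least 5 of 7 are present, otherwise missing. The same rule applies to baseline (as in Section 5.2) and to every post-baseline analysis week.

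This agrees with the baseline definition already in the SAP and covers the pruritus NRS, the VRS and the sleep disturbance NRS alike. It costs one sentence in the SAP and changes nothing in the data, the design or the sample size.
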